Effects of ambulation during the first stage of labour on maternal and neonatal

outcomes: A randomized controlled trial

Study Protocol with SAP

March 1, 2018

Effects of ambulation during first stage of labour on maternal and neonatal outcomes: A randomized controlled trial

Introduction

There is clear and important evidence that walking and upright positions in the first stage of labour reduces the duration of labour, the risk of caesarean birth, the need for epidural, (Lawrence, Lewis et al. 2013). In addition, ambulation and upright position have not been found to be associated with increased intervention or negative effects on mothers' and babies' wellbeing (Lawrence, Lewis et al. 2013). Women, particularly who have low risk labour, are highly advised to follow upright positions, and encouraged and assisted to assume whatever positions they choose (Lawrence, Lewis et al. 2013; Ondeck 2014).

Research confirms that movement is a safe and healthy coping strategy for pain, and confining labouring women to bed increases pain and decreases women's satisfaction with their birth experience (Romano and Lothian 2008; Ondeck 2014). An experimental study was conducted in Mangalore to examine the effect of ambulation during the first stage of labour on the intensity of labour pain, length of the first stage of labour, and use of analgesia, the study comprised of 40 primigravid mothers and they were grouped as experimental and control through randomization, experimental group received ambulation, the other group did not. Pain was assessed through Visual Analog Pain Scale and observational checklist was used to assess the outcome of labour there was a significant difference in duration of first stage of labour between the experimental and control group but no significant difference in overall outcome of labour. The mean pain

score for experimental group was (6.8) which was less than the main pain score of control group. The findings of the study revealed that ambulation was effective to reduce the intensity of labour pain among primigravid mothers (Savitha, Nayak et al. 2013).

Another experimental study was conducted to evaluate the effectiveness of back massage versus ambulation during first stage of labour among primigravid mothers in terms of pain and anxiety, an experimental research approach with pre-test post test control group design was undertaken on 90 primigravid mothers (30 in each experimental group1, experimental group 2 and control group). Purposive sampling technique was used to select the primigravid mothers. There was a significant difference in mean pre-test and post-test labour pain scores and anxiety scores during first stage of labour among primigravid mothers .It was concluded that back massage and ambulation was effective to reduce the level of labour pain and anxiety among primigravid mother during first stage of labour (Bala, Babu et al. 2017).

Ambulation and upright position were found to positively affect the progress of labour and a woman's behavioural response to childbirth. An updated systematic review of 25 studies with a total of 5218 women, done to assess the effects of upright positions(walking, sitting, standing, kneeling) versus recumbent positions (supine, semi recumbent, lateral) for women in the first stage of labour on the length of labour, and other outcomes. Results showed that the duration of labour was approximately one hour shorter for women randomized to upright as opposed to recumbent positions(Lawrence, Lewis et al. 2013).

A quasi experimental study conducted to determine the effectiveness of ambulation during first stage of labour, on the outcome of labour. A post test only control group design was used in 60 samples. Results revealed that ambulation during first stage of labour was effective in reducing duration of labour (t value = -2.27 and p value <0.05) also in bringing positive behavioural response (Mann-Whitney U test, p value< 0.05). Authors concluded that ambulation during first stage of labour was effective in reducing out good behavioural response in primigravid women. Also ambulation did not have any adverse effect on neonatal outcome. It was observed by the investigator that, having the choice to ambulate is well accepted by women when they were told the potential benefits of ambulation. Also it is a cost effective intervention which the nurse can implement independently (Prabhakar, George et al. 2015).

A systematic review of the effect of ambulation and maternal position during the first stage of labour on duration of this stage was done. All randomized controlled trials carried out to assess this effect were taken into consideration in this review. Authors concluded that adoption of the upright position or ambulation during first stage of labour may be safe, but considering the available evidence and its consistency, it cannot be recommended as an effective intervention to reduce duration of the first stage of labour(Souza, Miquelutti et al. 2006).

A randomized controlled trial was conducted to evaluate the vertical position adopted by nulliparous women during labour in terms of pain and satisfaction with the position. The study was based on a secondary efficacy analysis of data from 107 nulliparous women enrolled in which the vertical position adopted during the dilation phase of labour was evaluated. The analysis involved comparing the median percentages of the duration for which women remained in the vertical position for each of the variables studied. Results revealed that at 4 cm of dilation, the women with a pain score < 5 remained longer in the vertical position during labor compared to those with a score >7 (p=0.02). At 4 and 6 cm of dilation, the women who reported greater satisfaction remained more than 50% of the time in the vertical position (p=0.02 and p=0.03, respectively). Authors concluded that vertical position helped relieve labour pain and increased comfort and patient satisfaction (Miquelutti, Cecatti et al. 2009).

Significance of the study

Despite evidence in the literature that ambulation and upright positioning during labour does not harm mother, fetus, or newborn, there is evidence that women are still largely confined to bed during the first stage of labour(Simkin and Bolding 2004). The increased use of medical interventions such as epidural analgesia, continuous electronic fetal monitoring, intravenous infusions for fluids and electrolytes, and a restrictive birthing environment limits women's instinctive responses to labour pain and contractions rather than assisting the woman to cope with the pain and anxiety of labour (Simkin and Bolding 2004)

In Jordan practices in maternity wards are not based on best evidence(Shaban, Hatamleh et al. 2011). The majority of health facilities restrict movement during labour, women were confined to bed in the lithotomy position and most of these facilities strap women in the delivery position, women have no choice to assume the position they prefer during labour and delivery (Khresheh, Homer et al. 2007; Sweidan, Mahfoud et al. 2008; Shaban, Hatamleh et al. 2011). The practice of restricting women's movement in labour is contrary to the statements and recommendations of professional organizations advocate for women to move about during the first stage of labour, as long as they remain low-risk (WHO 1996; Ondeck 2014).

Implementing evidence-based maternity care in developing countries with limited resources such as Jordan is particularly challenging, and requires commitment to applying the most up to date evidence to clinical decisions.

Purpose of the study

The purpose of this study is to begin investigation that could help provide a better quality of care during birth and improve maternity outcomes in one Jordanian hospital. The process was introducing an evidence-based practice of encouraging women to ambulate and assume the upright position during the first stage of labour and observing if results would suggest low cost modifications for the maternity health service environment, especially the labour ward. This is the first study that has attempted to implement and evaluate such an intervention in Jordan. To examine the effect of ambulation (walking) during first stage of labour on maternal and neonatal outcomes.

Methods

Design

A randomised controlled study will be conducted with primiparous women who come to give birth at Al- Karak Hospital in Jordan. In the intervention group women will be encouraged to ambulate and women in the control group will receive usual maternity care. Women will be subsequently randomised into the groups using a table of random numbers. "Ambulation during labour" here will refer to moving from place to place during the first stage of labour that reduces the amount of time a woman spends laying down during this stage (measured by recording the number of minutes spend on walking).

Setting

The setting for this study will be the maternity ward at Al-Karak hospital, the main governmental and teaching hospital in the southern region of Jordan. In 2016 2,808 births occurred in this hospital, 59% were caesarean births (Ministry of Health 2017). In this hospital, the woman usually labours in 26- bed ward with restrictions on movement. This is consistent practice nationally. Certified midwives, resident physicians, and obstetricians provide care. Midwives in this hospital work with uncomplicated labours and help obstetricians with complicated cases.

Sample and sampling

We will recruit consecutive eligible women interested in participating in the study, for a period of one year. All primiparous women with uncomplicated singleton pregnancies between 37 and 41 weeks gestation, cephalic, with cervical dilatation 3 to 5cm who come to give birth at Al-Karak hospital, between the 1st of January and the 30th of December 2018 will be approached for participation.

Sample size

The sample size was calculated using the G power version 3.1. Based on difference between two independent groups, alpha= 0.05, median effect size 0.3, power =95%, sample size required for each group is 88 women. To overcome attrition, 25% of the calculated sample will be added, the final sample size will be 110 women in each group.

Data collection process

Data will be collected using structured tool developed by the researchers based on literature review of research related to the current topic (appendix 1). The tool composed of section collecting the socio-demographic data and another section collecting maternal and neonatal outcomes. The research tool was reviewed by a panel (n=3) of experts in maternity health field. Before starting the study, the final version of the tool will be tested in a pilot study to evaluate its feasibility, clarity, and reliability. Assistant researcher (midwife) will complete the first section of the tool, which related to socio-demographic data, and will allocate participants to control and intervention group according to the randomization list.

The principal researcher will be kept blind for those participants who are in the intervention and control groups. Completing the second part of the study tool, which is related to maternal and infant health outcomes, will be in maternal ward and by the primary investigators 24 to 48 hours after birth.

Outcomes Measurement

The study outcomes have two main aspects; related to maternal outcomes and neonatal outcomes. The maternal outcomes will include 1. Duration of the first stage of labour (defined as the time from the onset of regular contractions to the time of full cervical dilatation of 10 cm as documented by the midwife) 2. Intensity of labour pain (measured by the Visual Analogue pain Scale rating from 0 to 10 in which the woman registers the pain perception, considering 0 no pain and 10 the worst pain imaginable.) 3. Use of analgesics (defined as used or not used), 3. Mode of birth (defined as normal, vacuum extraction, forceps delivery, or cesarean section) 4. Woman satisfaction with the birth experience (measured by research-based birth satisfaction and dissatisfaction items from literature. Women will respond on a five-point Likert scale with agreements with the statement).

The new neonatal outcomes will include: 1. Apgar scores at 5 minutes

Data analysis

Data will be analysed using SPSS version 22. Descriptive statistics will be used to describe the sample characteristic. According to the level of measurement, independent *t*-test, and ANOVA will be used to examine the differences between study groups (intervention and control) based on baseline socio-demographic date and health

outcomes. Statistical assumptions will be checked and ensured, and results will be considered significant if P values were < 0.05.

Ethical consideration

Approval to conduct the study will be obtained from the ethics committee at faculty of nursing / Mutah University and the Ministry of Health (MOH). Women will be informed about the study and verbal and written consent for agreement will be obtained from each woman (appendix 2). Women will be assured that participation is voluntary and they have the right to withdraw from the study at any time without giving any reason. Women will be assured that their information will not be recognized in any products of this research.

References

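### Sample size: 88 women per group gives about 51% power for an effect size of 0.3 at two-sided alpha 0.05, not the stated 95%

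*Combined protocol and SAP*

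**What the plan says.** The Sample size section reports a G*Power 3.1 calculation. Its basis is given as "Based on difference between two independent groups" and its inputs and result as "alpha= 0.05, median effect size 0.3, power =95%, sample size required for each group is 88 women". It continues: "To overcome attrition, 25% of the calculated sample will be added, the final sample size will be 110 women in each group".

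The section does not say whether the test is one- or two-sided, which effect-size metric the 0.3 belongs to, or which outcome is being powered. The Data analysis section names the independent t-test and ANOVA for comparing intervention with control, and its only decision rule is "results will be considered significant if P values were < 0.05", with no direction given.

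**The concern.** For two independent means, a standardised difference of 0.3 with 95% power needs several hundred women per group, so 88 looks far too small at first sight.

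This paragraph is the plan's only justification of the trial's size. A reader who accepts it will believe that a real effect of 0.3 would be missed only one time in twenty, and could take a non-significant result as good evidence against an effect of that size. A null result is a realistic prospect: the protocol's own background includes a systematic review which concluded that ambulation could not be recommended as a way to shorten the first stage.

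**Working it through.** **Inputs.** From the Sample size section: alpha 0.05, effect size 0.3, power 95%, two independent groups, equal allocation, 88 per group, 110 after the allowance. From Data analysis: t-test and ANOVA, P < 0.05.

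**Assumptions where the plan is silent.** The 0.3 is read as a standardised mean difference d (SD = 1), because the stated basis is a two-group difference and a t-test is planned. Testing is taken as two-sided; one-sided figures are given alongside.

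**Step 1. Try to reproduce 88 from the stated inputs.** The normal approximation is n per group = 2 × ((z₁ + z₂)/d)², where z₁ is the critical value for alpha and z₂ = 1.645 for 95% power.

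- Two-sided (z₁ = 1.960): 2 × (3.605/0.3)² = 288.8, so 289. The exact noncentral t gives 290.
- One-sided (z₁ = 1.645): 2 × (3.290/0.3)² = 240.5, so 241. The exact noncentral t gives 242.

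Neither is near 88. The two-sided requirement is 290/88 = 3.3 times the stated number. Lowering the power does not close the gap: 80% power at d = 0.3 still needs 176 per group two-sided or 139 one-sided.

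**Step 2. Power that the stated numbers give.** Noncentral t with 2n − 2 degrees of freedom and noncentrality d × √(n/2). For n = 88 and d = 0.3 the noncentrality is 0.3 × √44 = 1.99, against a two-sided critical value of 1.974, so power is close to one half.

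| n per group | d | Power, two-sided | Power, one-sided |
|---|---|---|---|
| 88 | 0.3 | 50.8% | 63.2% |
| 88 | 0.4 | 75.1% | 84.1% |
| 88 | 0.5 | 91.0% | 95.1% |
| 110 | 0.3 | 60.1% | 71.7% |
| 110 | 0.5 | 95.8% | 98.0% |

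With 88 per group and a two-sided test, the detectable difference is d = 0.546 at 95% power and d = 0.425 at 80% power.

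**Step 3. Other readings of 0.3, all at 95% power and alpha 0.05.**

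| Reading of 0.3 | Required per group |
|---|---|
| Two-group ANOVA, f = 0.3 (d = 0.6) | 74 |
| Chi-square w = 0.3, 1 df (total 145) | 73 |
| Chi-square w = 0.3, 2 df (total 172) | 86 |
| Chi-square w = 0.3, 3 df (total 191) | 96 |

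None gives 88. The nearest, 86, needs an outcome with three categories compared between two groups. No listed outcome is defined that way: analgesic use has two categories (1 df) and mode of birth has four (3 df).

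**Step 4. Where 88 may come from.** For d = 0.5, alpha 0.05 and 95% power, the exact requirement is 88 per group one-sided (power 95.1%) and 105 two-sided. A second possibility is that 176, the per-group number for d = 0.3 at 80% power two-sided, was taken as a total and halved: 176/2 = 88. Both are inferences; the documents support neither directly.

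**Step 5. The attrition allowance.** 88 × 1.25 = 110, and 110 × 0.80 = 88. Adding a quarter therefore keeps 88 evaluable women for losses up to 20%. That arithmetic is sound as stated, but it does not restore the power: 110 per group with no loss gives 60.1% at d = 0.3.

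**The case against.** The strongest reply is that the plan leaves both the metric and the number of sides open, so 51% is conditional. One-sided power at 88 per group is 63%. If 0.3 were ANOVA f, and ANOVA is a named test, power would be about 98%. As chi-square w it would be 98%, 95.5% or 93% for 1, 2 or 3 df. That no chi-square test is named is weak evidence, since some outcomes are categorical and tests are to follow the level of measurement. On such readings the trial would be adequately, or nearly adequately, powered, and the fault would be one of reporting.

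Part of this stands. The 51% does rest on a two-sided test of a mean difference, and the origin of 88 cannot be proved. But the f and w readings fit the stated basis and the planned t-test less well, and none of them yields 88. Under the natural reading the 95% claim fails with either number of sides, even if all 110 women are analysed.

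It is also fair to say that the plan never claims its allowance covers a 25% loss, so the attrition point is a clarification and not an error. Finally, keeping 110 per group presumes that the sample size is right and the effect size wrong. The sponsor has to confirm that.

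**Conclusion.** The concern holds. Of the readings of the stated inputs that were tried, none produces 88 per group. With 0.3 as a standardised mean difference and two-sided testing, the trial has 50.8% power with 88 evaluable women per group and 60.1% with 110, where 95% is claimed. The risk of missing an effect of 0.3 is therefore 49% or 40%, not 5%. With a one-sided test the power is 63.2% or 71.7%, still far below the claim. The design is reasonable for a larger effect (91.0% power at d = 0.5 with 88 per group, two-sided). The paragraph must be corrected as written.

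**What to change.** If 110 per group is to stay, replace the power statement with one that the design supports. For example: *With 88 evaluable women per group (110 randomised, allowing up to 20% loss), a two-sided 5% t-test has 95% power for a standardised difference of 0.55, 91% for 0.5, and 51% for 0.3.* Remove the claim of 95% power at 0.3. State that testing is two-sided, that the effect size is a standardised mean difference, and which outcome the calculation serves.

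This costs one rewritten paragraph and no extra participants. The price is a less favourable stated detectable effect.

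If the sponsor confirms that a mean difference of 0.3 with 95% power is the real target, restating is not enough. The trial would need 290 evaluable women per group, or 290 × 1.25 = 362.5, so 363 per group, with the plan's own 25% addition.

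### The same role completes the baseline section and allocates from the randomisation list, with no concealment or list custody described: selection at entry is possible but not shown

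*Combined protocol and SAP*

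**What the plan says.** - **Sequence.** The Design section says: "Women will be subsequently randomised into the groups using a table of random numbers". It gives no blocking, stratification or ratio, and does not say who prepares the list. Sample size plans 110 women in each group.
- **Allocation.** Data collection process gives one role two tasks. "Assistant researcher (midwife) will complete the first section of the tool, which related to socio-demographic data", and the same role "will allocate participants to control and intervention group according to the randomization list".
- **Entry.** Sample and sampling says: "We will recruit consecutive eligible women interested in participating in the study". All eligible women are to be approached, and eligibility includes being a woman "with cervical dilatation 3 to 5cm who come to give birth at Al-Karak hospital". The documents do not name who screens, examines or enrols. Ethical consideration requires verbal and written consent but does not say who obtains it, or whether it comes before the list is consulted.
- **Blinding.** The only masking statement is: "The principal researcher will be kept blind for those participants who are in the intervention and control groups".
- **Outcome and analysis.** Outcomes Measurement defines first-stage duration as "the time from the onset of regular contractions to the time of full cervical dilatation of 10 cm as documented by the midwife". Data analysis names the t-test and ANOVA to "examine the differences between study groups (intervention and control) based on baseline socio-demographic date and health" outcomes. No adjustment for prognostic factors is mentioned.

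**The concern.** Random generation makes a sequence fair. Concealment keeps it fair by ensuring that nobody who can influence entry knows the next assignment. The plan covers the first and is silent on the second. Followed as written, allocation means consulting a list, and nothing stops the allocator from seeing the entries that come next.

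Women cannot be blinded to whether they are walking, so concealment at entry is one of the few protections this trial can have. Two entry conditions leave room for judgement: whether a woman is interested, and whether her dilatation falls within 3 to 5 cm. If someone who knew the next assignment could also influence either of these, the arms could differ before any ambulation took place. The analysis as described has no step that would remove such a difference.

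**Working it through.** No figure in the plan is in dispute. The check sets the sections side by side and follows the consequence for the duration outcome.

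**1. Does any statement hide the next assignment from the allocator?**

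| Statement | What it protects | Hides the next assignment? |
|---|---|---|
| Table of random numbers (Design) | How the sequence is generated | No; a random list can still be read ahead |
| Principal researcher kept blind (Data collection process) | Knowledge of group after assignment, for that person | No; the allocator is a different role |
| Consecutive recruitment, all eligible women approached (Sample and sampling) | Limits discretion over who is approached | No |
| Randomised subsequently; baseline section listed before allocation | Suggests an order of steps | No; neither consent nor eligibility is said to be fixed before the list is seen |

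Envelopes, central or telephone allocation and custody of the list appear nowhere. Appendices 1 and 2 are not in the copy reviewed, but they are cited as the data tool and the consent form, not as the randomisation procedure.

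**2. Is the route to selection complete?** It needs one party who both sees the list and influences entry. The documents give the allocating role two tasks, the socio-demographic section and allocation. They do not give it screening, cervical assessment or consent, and they do not give those tasks to anyone else. The route is open but not established.

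**3. Could assignments be predicted without seeing the list?** Blocking is not mentioned. The target is 110 per group, from 88 × 1.25 = 110, so 2 × 110 = 220 in total. If each of 220 women were allocated 1:1 without restriction, the chance of exactly 110 and 110 is C(220,110) / 2^220 ≈ 1/√(π × 110) ≈ 0.054, or 5.4%. If equal groups are to be guaranteed, some restriction or the closing of a full arm would be needed, and late assignments could then be predictable. If 110 is only a target, they need not be. The documents do not settle this.

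**4. How would a steered difference reach the outcome?** Write duration as D = E + R, where E is the time from onset of regular contractions to allocation and R is the time from allocation to full dilatation. E is fixed before allocation, so ambulation cannot change it. Then

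mean(D, ambulation) − mean(D, control) = difference in mean E + difference in mean R.

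A difference in mean E enters the comparison minute for minute. Selection could also change R, so the net bias could be larger or smaller. No section gives timings. That E is usually above zero at 3 to 5 cm is an inference from the entry criterion.

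**5. Would the planned baseline comparison catch it?** It is described as covering socio-demographic data. Dilatation must be assessed because it is an entry criterion. Whether it or onset time is recorded at entry depends on appendix 1, which was not available.

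**Separate illustration, not an estimate for this trial.** Assume selection shifts the outcome by d SD, there is no true effect, and a two-sided t-test is done at 0.05. With noncentrality d × √(n/2), the false-positive rates are:

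| Assumed d | 110 per group | 88 per group |
|---|---|---|
| 0.05 | 6.6% (ncp 0.371) | 6.3% (ncp 0.332) |
| 0.1 | 11.4% (ncp 0.742) | 10.1% (ncp 0.663) |
| 0.2 | 31.5% (ncp 1.483) | 26.1% (ncp 1.327) |

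Any bias of the same size would give these rates, whatever its source. Here d is a shift in the outcome. An equal imbalance in a baseline item would generally shift the outcome by less, in proportion to its correlation with the outcome.

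**The case against.** The strongest case for the plan is that this is a short protocol and silence on custody may be only a reporting gap. Recruitment is consecutive, every eligible woman is to be approached, the sequence is random, and the wording suggests that randomisation follows entry. The allocating role is not said to screen or take consent, so the party who might see the list may have no say over who enters.

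Much of this stands. It limits the conclusion to a possibility, and it means the first request should be to state the procedure if a concealed one exists. It does not remove the point. The plan does more than stay silent: it states a procedure, allocation according to the list, and it does not separate allocation from enrolment.

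A reader might infer several stronger things that the documents do not support:

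- **That the midwife knows upcoming assignments, or that selection takes place.** No section says so.
- **That one individual does all of this.** The text uses the singular for a role, recruitment runs for a year, and no headcount is given.
- **That the next assignment cannot be guessed because blocking is not mentioned.** This would favour the plan, but silence on blocking is not evidence that there is none.
- **That the illustrative percentages measure this trial's bias.** They rest on assumed shifts.

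**Conclusion.** The point holds as a gap in the design as written: the same role completes the baseline section and allocates from the list, and neither concealment nor custody is described. Selection at entry is possible on the condition that whoever sees the list also influences entry. The documents do not confirm or exclude that condition. The size of any resulting bias cannot be derived from them.

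The consequence is clearest for first-stage duration, because a steered difference in time elapsed before entry would be counted as part of the outcome. That step assumes contractions usually begin before allocation at 3 to 5 cm. The plan should be changed on this point, because analysis cannot restore concealment afterwards. Confidence is medium, since an undescribed procedure may exist. The gap does not show that the randomisation is invalid.

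**What to change.** If a concealed procedure already exists, describe it and say who holds the list. Otherwise:

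1. An existing team or faculty member who does not enrol, allocate or assess outcomes keeps the list. That such a person is available is an assumption.
2. That person prepares about 220 sequentially numbered, opaque, sealed envelopes from it.
3. The midwife opens the next envelope only after eligibility, consent, the baseline section, cervical dilatation and the time of onset of regular contractions have been recorded. She writes the woman's ID and the time on the envelope.
4. The protocol states who holds the list, whether allocation is restricted, and who screens and takes consent.
5. The stated recruitment window opens on 1 January 2018 and the document is dated 1 March 2018, so some women may already have been allocated. If so, use this procedure for the remaining women and report how the earlier women were allocated.

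The cost is a little preparation time, about 220 envelopes, two items recorded at entry and one protocol paragraph. Care, sample size and the planned tests do not change.

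### First-stage duration is timed from contraction onset although women are randomised at 3 to 5 cm, so the outcome carries pre-randomisation labour of unknown length that normally costs precision

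*Combined protocol and SAP*

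**What the plan says.** Outcomes Measurement lists duration of the first stage as the first maternal outcome, "defined as the time from the onset of regular contractions to the time of full cervical dilatation of 10 cm", with the midwife as the source of the record.

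Sample and sampling restricts recruitment to primiparous women "with cervical dilatation 3 to 5cm who come to give birth at Al-Karak hospital". The Design section adds: "Women will be subsequently randomised into the groups using a table of random numbers". It describes the intervention as "moving from place to place during the first stage of labour that reduces the amount of time a woman spends laying down during this stage"; as an allocated treatment, this can start only after randomisation.

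Sample size works on a standardised scale: "alpha= 0.05, median effect size 0.3, power =95%, sample size required for each group is 88 women", and then "25% of the calculated sample will be added, the final sample size will be 110 women in each group". It does not name the outcome to which the effect size belongs and gives no SD.

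Data analysis names the independent t-test and ANOVA. It mentions no covariate, and no section defines a duration that starts at randomisation. The data collection tool (appendix 1) is not in the text available, so nothing is claimed here about which fields it contains.

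**The concern.** The outcome clock and the randomised comparison start at different times. For a woman who arrives in labour at 3 to 5 cm, the recorded duration is the sum of two parts: labour before randomisation, which allocation cannot change, and labour from randomisation to 10 cm, which it can. Only the second part can carry a treatment effect. The first part normally adds spread, so the same difference in hours is tested against a larger SD.

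What is at stake is precision on the first-listed outcome: a real benefit of walking becomes easier to miss. The validity of the randomised comparison is not at stake.

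**Working it through.** **The plan's own figure.** For two independent means, n per group = 2(z₁ + z₂)²/d².

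- d = 0.3, two-sided 5%, 95% power: 2(1.960 + 1.645)²/0.09 = 289 (290 by exact t).
- d = 0.3, one-sided: 2(1.645 + 1.645)²/0.09 = 241 (242 by exact t).
- d = 0.5, one-sided: 2(1.645 + 1.645)²/0.25 = 87 (88 by exact t).

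So 88 does not follow from an effect size of 0.3; it matches 0.5 one-sided. With 88 per group and d = 0.3, two-sided power is 51%. The step to 110 is 88 × 1.25. The mismatch is a separate matter, but it means the plan shows no spare power.

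**Inputs for the effect of the clock.**

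- Effect: 1 h, from the review cited in the Introduction, in which "the duration of labour was approximately one hour shorter for women randomized to upright as opposed to recumbent positions". The protocol does not say which clock that review used. Assigning the full hour to post-randomisation time is an assumption.
- n: 110 per arm (Sample size), with 88 as the figure before the attrition allowance.
- Two-sided alpha 0.05. The plan does not state sidedness.
- SD of time from randomisation to 10 cm: 3 h, assumed.
- SD of labour before randomisation, s: 1, 2, 3 or 4 h, assumed.
- Correlation between the two parts, ρ: 0, +0.3 or −0.3, assumed.

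**Mean difference.** Total = pre + post. Randomisation gives both arms the same expected pre, so the expected difference in total equals the expected difference in post: 1 h on either clock.

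**Spread.** SD_total = √(3² + s² + 2·ρ·3·s); standardised effect = 1/SD_total; standard error of the difference = SD × √(2/110).

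- From randomisation: SD 3.00 h, d = 0.33, standard error 0.40 h, power 69%.
- From contraction onset, s = 3 and ρ = 0: SD = √18 = 4.24 h, d = 0.24, standard error 0.57 h, power 41%.

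Power from contraction onset, two-sample t-test, 110 per arm (reference 69%):

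| Pre-entry SD (h) | ρ = 0 | ρ = +0.3 | ρ = −0.3 |
|---|---|---|---|
| 1 | 65% | 58% | 73% |
| 2 | 54% | 44% | 67% |
| 3 | 41% | 33% | 55% |
| 4 | 31% | 26% | 42% |

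At ρ = 0 the variance is multiplied by 10/9 = 1.1, 13/9 = 1.4, 18/9 = 2.0 and 25/9 = 2.8.

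At 88 per arm the reference is 59%. At ρ = 0 it becomes 55%, 45%, 34% or 26%.

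**When there is no loss.** Variance rises only if s² + 6ρs > 0, that is s > −6ρ. At ρ = −0.3 the threshold is s = 1.8 h, which is why the 1 h row shows a slight gain and the 2 h row a slight loss.

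**What adjustment recovers.** Once elapsed labour is a covariate, regressing total or post-randomisation time on arm gives the same treatment estimate, because the two outcomes differ exactly by that covariate. The residual SD is 3√(1 − ρ²): 3.00 h at ρ = 0 and √8.19 = 2.86 h at ρ = ±0.3. Power is then 69% and 73%, whatever s is.

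**The case against.** The strongest case for leaving the plan alone is that contraction onset to 10 cm is a recognisable measure of the whole first stage, suits the stated aim, and gives a valid randomised comparison. That stands. It is why replacing the definition is only one of two acceptable remedies.

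It also stands that the size of the loss is not established. Every SD and correlation above is assumed. Entry anywhere from 3 to 5 cm pushes the correlation downwards, since a woman entering at 5 cm has more labour behind her and less ahead. The net sign is unknown, and with a small pre-entry spread the loss is a few points or none.

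Several stronger readings are tempting, and the documents do not support them:

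- *The effect in hours is diluted or biased.* It is not; randomisation balances earlier labour in expectation. Only the standardised effect and the precision change.
- *Chance imbalance in earlier labour could pass for an effect.* That variation is already in the t-test's standard error, and the 5% error rate holds. This is the same loss of power described twice.
- *The outcome includes hours of labour, mostly before admission and timed by the woman's recollection.* No section gives the length of this period, where it was spent, or how onset is established beyond the midwife's record.
- *Onset recorded with knowledge of the arm biases the result.* Data collection process blinds only the principal researcher, and an assistant midwife allocates from the list, so this is possible. But no section says when onset is written down, so it is a reason to fix the order of recording and not a demonstrated bias.

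**Conclusion.** The mismatch between the outcome clock and the point of randomisation is certain from the text wherever regular contractions precede allocation, and the planned analysis does nothing about it. The consequence is an avoidable loss of precision, probable but of unknown size. Under the stated assumptions at 110 per arm, power moves from 69% to between 26% and 73%; eleven of the twelve combinations examined show a loss and one a small gain. Confidence is high in the mismatch and low in any single power figure. The primary comparison would remain valid if nothing changed, so this is a worthwhile cheap improvement and not a fatal flaw.

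**What to change.** Before the allocation is looked up, record three items for each woman: the clock time of randomisation, the reported onset of regular contractions, and cervical dilatation at entry. Then state one of these in the analysis plan:

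1. Define outcome 1 as time from randomisation to 10 cm, compare arms adjusting for entry dilatation, and keep duration from contraction onset as a secondary measure for comparison with the literature.
2. Keep the present definition and compare arms adjusting for labour already elapsed at randomisation and for entry dilatation. Use the same recorded onset for the outcome and for elapsed labour, so that error in it cancels.

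The cost is one or two extra form fields, since dilatation is already assessed for eligibility, and a regression model or analysis of covariance in place of the plain t-test. Under the first option the main figure is no longer the whole first stage. Neither option alters care or recruitment.
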